3.3.6. Alternative Dosing Schedules

Alternative schedules may be evaluated based on emerging data. Less frequent dosing schedules (e.g., once weekly) may be implemented without an amendment if emerging data suggest that twice weekly administration will result in excessive toxicity or if PD data suggest less frequent administration may be warranted. In this case, the starting dose would be one dose level above the highest dose which has been determined to be tolerable when administered twice weekly. In addition, alternative dosing schedules which result in increased frequency of administration may be considered if the safety, PK, and PD data suggest that a sufficient therapeutic exposure cannot be achieved using the initial dosing schedule; this would require a protocol amendment. Dose escalation will continue using the guidelines outlined in [Table 2](#).

3.3.7. Part 1: Futility and Efficacy Analysis for GCB-DLBCL Subjects

There will be a GCB-DLBCL expansion cohort enrolled after the completion of dose escalation in Part 1. For the GCB-DLBCL expansion cohort in Part 1, futility and efficacy evaluation of overall response data will be performed in order to support the early decision regarding opening Part 2 dose expansion. The methodology is based on the Bayesian predictive probability of success if enrollment continues until all planned subjects are recruited [[Lee, 2008](#)]. Details of the predictive probability methodology, futility and efficacy evaluation are explained in Section 12.2.1.2. In summary, a minimum of 13 and maximum of 27 GCB-DLBCL patients will be enrolled. Once 13 GCB-DLBCL patients at MTD/RP2D have been enrolled (including patients in dose escalation phase) and have completed response assessments of safety and efficacy, response data will be reviewed on an ongoing basis for evidence of futility or efficacy.

For futility/efficacy analysis, subjects evaluable for response assessment will be defined by any or all of the following criteria:

- Subjects who have at least two post-baseline radiological disease assessments and have been on study for at least 28 days (one cycle)
- Subjects who have progressed or have died or have withdrawn from study treatment due to any reason.

Interim analysis (IA) of futility and efficacy can be conducted at any time after 13 GCB-DLBCL subjects have enrolled and are evaluable for response assessment. If the thresholds for futility are met, the Part 1 expansion cohort may be stopped based upon the evaluation of the totality of the data. If the efficacy thresholds are reached, then Part 2 expansion may be opened. If neither futility nor efficacy thresholds are met at any interim analysis, and the totality of the data does not support continuation of the trial, then the trial may be terminated. All available data will be considered in making decision of termination or continuation of the trial.

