7.7. Evaluation of Anti-Cancer Activity

Disease assessment may include imaging and physical examination (as indicated for palpable/superficial lesions). Refer to [Appendix 4](#) for more details on response assessment criteria.

- Disease assessment for lymphomas will be completed within 4 weeks of first dose of GSK2816126 and repeated 8 weeks after dosing is initiated, every 12 weeks thereafter, and at the final study visit.
- Disease assessment for solid tumors will be completed within 4 weeks of first dose of GSK2816126 and repeated every 8 weeks after dosing is initiated, and at the final study visit.
- Disease assessment for MM will be completed within 4 weeks of first dose of GSK2816126, week 4 and repeated every 6 weeks thereafter.

See the Time and Events Table (Section [7.1](#)) for the schedule of assessments of anti-cancer activity. Assessments must be performed on a calendar schedule and should not be affected by dose interruptions/delays. For post-baseline assessments, a window of ± 7 days is permitted to allow for flexible scheduling. If the last radiographic assessment was more than 8 weeks prior to the subject's withdrawal from study and progressive

disease has not been documented, a disease assessment should be obtained at the time of withdrawal from study.

For subjects with NHL, the following B symptoms should be assessed at the time points in the Time and Events Table (Section 7.1):

- night sweats without signs of infection
- unintentional weight loss of $\geq 10\%$ within the previous 6 months
- recurrent, unexplained fever of greater than 38°C for 2 weeks without signs of infection

If a lymphoma subject had involvement of bone marrow at baseline, and a CR is suspected, a bone marrow biopsy must be obtained. A repeat bone marrow biopsy will be performed within 8 weeks of the imaging confirmed CR in accordance with the response guidelines. See [Appendix 4](#): Section 15.4 for additional details.

Tumor response will be assessed as outlined above and in the Time and Events Schedule by the investigator using:

- Lymphoma Subjects: Revised Response Criteria for Malignant Lymphoma (RRCLM)([Appendix 4](#))
- Solid Tumor RECIST 1.1 ([Appendix 5](#))
- Multiple Myeloma: International Myeloma Working Group (IMWG) ([Appendix 6](#))
- Prostate: RECIST 1.1 and PSA ([Appendix 7](#))

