$$H_0: p \leq 20\%$$

The alternative hypothesis is:

$$H_A: p \geq 40\%$$

As listed in [Table 16](#), the futility/efficacy evaluation will start with 13 subjects and allow for maximum of 27 subjects (including GCB-DLBCL subjects enrolled at the RP2D in the dose escalation phase.) This design will have a type I error rate (α) of 0.087 and a power of 0.803. In this particular expansion part, the trial is designed to allow stopping for both futility and efficacy. The trial may be stopped early for futility if the predictive probability of the overall response rate greater than the null hypothesis of 20% is very low, i.e. below 5.0% for this design, and may be stopped early for efficacy if the predictive probability of the overall response rate greater than 20% is very high, i.e. 90.0% or above. The type I error rate, power, and predictive probability of success were derived by explicitly stating null and alternative hypothesis of response rate, the minimum and maximum sample size, futility and efficacy stopping boundaries and the selection of the optimizing criterion as the maximization of power under the alternative hypothesis. The Bayesian prior used in determining the design was Beta (0.15, 0.85), a distribution with a mean response rate of 15%. Under the null hypothesis, that is, if the true response rate is 20%, the expected sample size of the design is 16.48 subjects and probability of early termination (PET) is 96.3%. Under the alternative hypothesis, that is,

if the true response rate is at least 40%, the expected sample size of the design is 16.98 subjects and PET is 94.7%.

The input parameters for finding the design shown in [Table 16](#) are:

Nmin	13
Cohort	1
Nmax	27
theta_Lbegin	0.05
theta_Lend	0.05
theta_Lstep	0.001
theta_Upper	0.9
theta_Tbegin	0.9
theta_Tend	0.9
theta_Tstep	0.001
p_0	0.2
p_1	0.4
Prior a0	0.15
Prior b0	0.85
Type I Error	0.1
Power	0.8

Table 16 Stopping Rules for GSK2816126 Part 1 GCB-DLBCL Cohort Expansion

No. of Subjects Evaluated for Response	Stopping Criteria [1]	
	Stop for Futility if No. of Responders (CR+PR) Less Than or Equal To This Number	Declaration of Efficacy if No. of Responders (CR+PR) Greater Than or Equal To This Number
13	2	6
14	2	7
15	2	7
16	3	7
17	3	7
18	3	8
19	4	8
20	4	8
21	5	8
22	5	9
23	5	9
24	6	9

No. of Subjects Evaluated for Response	Stopping Criteria [1]	

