To be assigned a status of partial response, all changes must be confirmed by repeat assessments performed no less than four weeks after the criteria for PR were met.

1. At least a 50% decrease from baseline in the SPD of up to six of the largest dominant nodes or nodal masses.

2. No increase in the size of the liver or the spleen. No unequivocal progression in any nonmeasurable or nondominant site.
3. Splenic and hepatic nodules must regress by $\geq 50\%$ in SPD compared to baseline. If only a single nodule/lesion, it must regress by $\geq 50\%$ in the greatest transverse diameter compared to baseline.
4. With the exception of splenic and hepatic nodules, involvement of other organs is accessible and no measureable disease should be present.
5. Bone marrow assessment is not relevant for determination of a PR if the sample was positive prior to treatment. However, if positive, the cell type should be specified. Subjects who achieve CR criteria above, except for persistent morphologic bone marrow involvement will be considered partial responders. When the bone marrow was involved before therapy and a clinical CR was achieved, but no bone marrow assessment after therapy, subjects must be considered partial responders.
6. No new sites of disease must be observed.
7. When performed, positron emission tomography (PET) must be positive in at least one previously involved site.

Stable Disease

Neither sufficient shrinkage to qualify for a CR or PR nor sufficient increase to qualify for progressive disease taking as reference the smallest SPD since the treatment started.

When performed, PET should be positive at prior sites of disease with no new areas of involvement on the CT or PET.

Relapsed Disease (after CR)/Progressive Disease (after PR, SD)

Criteria for determining PD for new lesions and target lesions are shown in [Table 19](#):

Table 19 Criteria for determining PD for new lesions and target lesions

	Nodes	Extranodal ('liver/spleen' & 'other' categories)

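### Section 3.3.7 lets outcome decide when a subject is counted, so the stated type I error of 0.087 and power of 0.803 are not properties of the Table 16 rule as written

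*Protocol*

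**What the plan says.** Protocol section 3.3.7 gives two routes to being evaluable for the GCB-DLBCL expansion cohort. The first is "Subjects who have at least two post-baseline radiological disease assessments and have been on study for at least 28 days (one cycle". The second is "Subjects who have progressed or have died or have withdrawn from study treatment due to any reason", with no minimum time and no scan required.

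Section 7.7 and the Time and Events table set the lymphoma imaging: within 4 weeks before first dose, then "repeated 8 weeks after dosing is initiated, every 12 weeks thereafter, and at the final study visit". It adds: "For post-baseline assessments, a window of ± 7 days is permitted to allow for flexible scheduling". The second scheduled post-baseline scan therefore falls at week 8 + 12 = 20, give or take a week.

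Appendix 4 has a confirmation rule: "To be assigned a status of partial response, all changes must be confirmed by repeat assessments performed no less than four weeks after the criteria". The same applies to complete response. No early confirmation scan is scheduled, but one at about week 8 + 4 = 12 would be allowed.

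On the trigger, section 3.3.7 allows a look at any point from 13 GCB-DLBCL subjects who are both on the trial and evaluable. Table 16 is indexed by the number of subjects evaluated, from 13 to 27. Nothing says that the subjects counted must be consecutive by enrolment, or that earlier subjects still pending must be resolved first. Section 12.2.1.2 states for this design a type I error "of 0.087 and a power of 0.803".

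**The concern.** The operating characteristics in section 12.2.1.2 come from a binomial model in which the first n outcomes are an unselected sample. The evaluability definition breaks that condition. A subject who fails in week 3 is counted in week 3, while a subject treated on the same day who responds at week 8 is counted at about week 12 or week 20. At any look while accrual continues, the pending subjects are not a random subset.

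On the scheduled scans the early counts over-represent failures, which pushes the observed response rate down towards the futility boundary. This cohort informs whether Part 2 opens, so the main risk is a false negative for an active drug.

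**Working it through.** **Inputs from the protocol (12.2.1.2, 3.3.7, 7.7).** Null response rate 20%, alternative 40%; looks after every subject from 13 to 27; prior Beta(0.15, 0.85); lower and upper predictive-probability limits 0.05 and 0.9; final posterior limit 0.9; the Table 16 boundaries (for example, at 13 evaluated: futility at 2 or fewer, efficacy at 6 or more); scans at weeks 8 and 20.

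**Step 1: reproduce the plan's figures.** The predictive probability with x responders among n is

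PP(n, x) = Σ over y of BetaBin(y; 27−n, 0.15+x, 0.85+n−x) × 1{Pr(p > 0.2 | Beta(0.15+x+y, 0.85+27−x−y)) > 0.9}.

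Stopping for futility at PP < 0.05 and for efficacy at PP > 0.9 regenerates every row of Table 16. Carrying the binomial distribution forward, P(n, x) = (1−p)·P(n−1, x) + p·P(n−1, x−1), and removing paths that hit a boundary gives:

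| | p = 0.20 | p = 0.40 |
|---|---|---|
| Probability of declaring efficacy | 0.0865 (stated 0.087) | 0.8031 (stated 0.803) |
| Expected number evaluated | 16.48 | 16.98 |
| Early termination | 96.3% | 94.7% |

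All stated values are reproduced. They are correct for outcome-independent ordering.

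**Step 2: apply the same boundaries in order of evaluability.** The protocol gives neither accrual nor time to failure, so these are assumptions: Poisson accrual of 0.5 to 4 per month; 30% to 90% of non-responders failing at a time uniform over weeks 2–8; all other non-responders counted at week 20. There were 20,000 simulated trials per cell, so the standard error near 0.8 is √(0.8×0.2/20,000) ≈ 0.003.

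Power at 40%, responders counted at week 20:

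| Non-responders failing by week 8 | 0.5/month | 1/month | 2/month | 4/month |
|---|---|---|---|---|
| 30% | 0.792 | 0.782 | 0.766 | 0.725 |
| 50% | 0.787 | 0.766 | 0.724 | 0.621 |
| 70% | 0.784 | 0.750 | 0.672 | 0.482 |
| 90% | 0.768 | 0.727 | 0.612 | 0.325 |

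If the early failures all surface at the week-8 scan instead, the ranges are 0.771–0.799, 0.742–0.789, 0.669–0.774 and 0.435–0.734. Taking both timings together and allowing about 0.01 between runs, power is 0.77–0.80, 0.73–0.79, 0.61–0.77 and 0.32–0.72. Type I error falls as well, to 0.01–0.08.

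The mechanism shows in the first 13 evaluable. At 2 per month with 70% early failures, their mean response rate is 31.0% against a true 40%, that is 13 × 0.310 = 4.0 responders instead of 13 × 0.40 = 5.2.

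**Step 3: responders counted at week 12.** Responders now precede non-responders with stable disease, who still wait until week 20.

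| Non-responders failing by week 8 | Power, 0.5 / 1 / 2 / 4 per month | Type I error, same order |
|---|---|---|
| 50% | 0.804 / 0.809 / 0.808 / 0.819 | 0.086 / 0.086 / 0.089 / 0.097 |
| 70% | 0.801 / 0.791 / 0.781 / 0.758 | 0.084 / 0.081 / 0.075 / 0.070 |
| 90% | 0.795 / 0.778 / 0.741 / 0.667 | 0.078 / 0.072 / 0.066 / 0.046 |

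With only 30% early failures the bias reverses, reaching power 0.86 and type I error 0.14 at 4 per month. The overall ranges are 0.66–0.86 and 0.04–0.14.

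**Step 4: count in enrolment order.** With the same simulated subjects taken in order of entry, power is 0.803 (100,000 runs) and type I error about 0.086. The departure therefore comes from counting order alone.

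**The case against.** **Confirmation scan.** A scan near week 12 satisfies both the confirmation rule and the two-scan rule, and then the loss can vanish. This stands, and it rules out saying that power is necessarily lost. It does not rescue the stated figures: at week 12 they hold only for some mixes of early failure and stable disease, and in others type I error exceeds the 0.1 ceiling in section 12.2.

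**Opposing sentence in 3.3.7.** Review is to begin once 13 patients are enrolled and have completed response assessments, which could mean the first 13 enrolled. Holding the first look until those 13 are all evaluable, then counting by evaluability, gives power with week-20 responders of 0.78–0.79, 0.75–0.79, 0.69–0.77 and 0.56–0.76 at 0.5, 1, 2 and 4 per month. That softens the problem without curing it.

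**Non-binding futility.** A boundary only permits stopping, after review of all data, and in an open-label study pending responses can be seen. If futility is never acted on, power is at least 0.816 (9 or more of 27). A reader might infer that an active drug would be stopped mechanically; the documents do not support that. Still, 0.803 is stated for the rule as followed.

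**Deferral to the Reporting and Analysis Plan.** Section 12.3.4.1 leaves interim procedures there. But the protocol itself fixes both the evaluability definition and the operating characteristics, and these two do not match.

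**Expected sample sizes.** A reader might infer that "the expected sample size of the design is 16.48 subjects" is wrong because more subjects will have been enrolled by then. It is not an error: Table 16 is labelled by subjects evaluated, and the figure reproduces.

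**Part 2.** A reader might extend the fault to Tables 17–18 or to the myeloma cohort. The definition is written for Part 1 GCB-DLBCL only, and only Table 16 was simulated.

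**Conclusion.** The point holds in limited form. Section 3.3.7 makes the time of counting depend on outcome and sets no enrolment-order rule, so 0.087 and 0.803, though arithmetically correct for the model used, do not describe the rule as written.

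On scheduled scans the simulated power is below 0.803 throughout. The shortfall is up to about 3.5 points at 0.5 per month and grows with accrual and with early failure. The lowest value, 0.32, needs 4 per month and 90% early failure together. Type I error is then conservative. With confirmation scans near week 12, the departure may be nil, a loss, or a gain in power with inflated type I error. All sizes rest on assumed accrual and failure timing.

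Given the small effect at slow accrual and the non-binding futility rule, this should be fixed before the first look but does not invalidate the design.

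**What to change.** In sections 3.3.7 and 12.2.1.2, state that Table 16 is applied to the first n GCB-DLBCL subjects in order of first dose, and that the look at n is taken only when all n have a final outcome: confirmed response, second post-baseline assessment without response, or progression, death or withdrawal. The stated 0.087 and 0.803 then hold with no change to any boundary. The alternative is to keep the definition and restate the operating characteristics under it, giving the accrual and timing assumptions. If the same evaluability definition is used in Part 2, carry the ordering rule to Tables 17–18.

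The cost is one paragraph of text. Each look waits for the slowest of the first n subjects, so a few more are enrolled meanwhile: about three more at a null stop with accrual of 2 per month.

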3.4. Part 2: Expansion Cohorts

Part 2: Expansion Cohorts in both wild type and EZH2 mutation-positive GCB-DLBCL and tFL subjects, and subjects with MM

The primary objective of Part 2 is to investigate whether administration of GSK2816126 at the RP2D has a potentially clinically meaningful activity for more tumor types, if notable response rate is observed in Part 1 expansion cohort of GCB-DLBCL patients. Expansion cohorts will be enrolled in Part 2, including GCB-DLBCL and tFL patients with mutant and wild type EZH2 and patients with MM. Similar to Part 1 expansion design, Part 2 expansion design is planned based on predictive probability methodology. Rather than early stop for either futility or efficacy, Part 2 allows early stop for futility only. For each expansion cohort of GCB-DLBCL and tFL patients, a minimum of 10 and maximum of 32 patients will be enrolled at the RP2D. For MM cohort, a minimum of 14 and maximum of 40 patients will be enrolled at the RP2D. Interim analysis of response data will start from minimum number of patients enrolled and at any time thereafter. Details of Part 2 designs and stopping criteria are elaborated in Section 12.2. All available data will be considered in making decision of termination or continuation of the trial.

It is noted that patients with GCB-DLBCL, tFL and MM enrolled at MTD/RP2D in the previous stages of the trial (dose escalation and cohort expansion in Part 1) will be included for the Part 2 analysis.

3.4.1. Part 2 PK/PD cohort:

In Part 2 a cohort of up to 12 subjects may be enrolled at RP2D to collect adequate data on safety, pharmacokinetics, or pharmacodynamics. Urine, bile, and additional blood samples may be collected following repeated administration for drug metabolite profiling and to obtain information on renal excretion of GSK2816126. Mandatory collection of pre- and post-treatment tumor biopsies will be required for enrollment in a PK/PD cohort

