7.6.1.1. GCB-DLBCL Subtyping (DLBCL subjects only)

Central confirmation of GCB DLBCL status will be confirmed by an IHC test utilizing the Choi algorithm [Choi, 2009] in Part 1 and 2.

Local testing, in advance of central confirmation may be performed to determine GCB status for enrollment using the Choi algorithm or a suitable alternative algorithm.

7.6.1.2. EZH2 Mutation Analysis (required for study entry in Part 2 for GCB-DLBCL and tFL subjects only)

Screening for eligibility for Part 2 of the study will be conducted using either an NGS-based gene panel or a custom quantitative real time polymerase chain reaction (RT-PCR) test based on TaqMan PCR chemistry. Both tests detect 7 known activating mutations in the EZH2 gene: Y641F (c.1937A>T); Y641N (c.1936T>A); Y641S (c.1937A>C); Y641H (c.1936T>C); Y641C (c.1937A>G); A677G (c.2045C>G); and A687V (c.2075C>T) .

EZH2 mutation analysis on archival tumor samples or fresh biopsies from subjects enrolled in Part 1 may also be performed, though the presence of an EZH2 mutation is not required for study entry in Part 1.

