12.2. Sample Size Determination

The sample size planned for Part 1 arises from the predefined criteria for dose selection and is not driven by statistical considerations.

In addition, Part 1 expansion may include up to 27 GCB-DLBCL subjects at MTD/RP2D twice-weekly for 3 out of 4 weeks followed by 1 week off. This will allow futility/success analysis with type I error rate no more than 0.1 and at least 80% of power. Additionally, 15 subjects with solid tumors or prostate cancer may be enrolled for the evaluation of safety, futility and efficacy.

The additional 168 subjects in Part 2 of the study (which includes up to 32 subjects each for the EZH2 mutant and EZH2 WT GCB-DLBCL populations, and up to 32 subjects each for EZH2 mutant and EZH2 WT tFL populations as well as up to 40 MM subjects) will provide additional safety and tolerability information about the treatment and a better precision around the response rate estimate.

Approximately 168 subjects will be enrolled in Part 2 in five expansion cohorts: two GCB-DLBCL cohorts with up to 32 subjects from the EZH2 wild-type population, and up to 32 subjects from the EZH2 mutation positive population, and two tFL cohorts with up to 32 subjects from the EZH2 wild-type population and up to 32 subjects from the EZH2 mutation positive population and up to 40 subjects in the MM cohort. Additional subjects/cohorts may be enrolled to allow for evaluation of additional dose levels.

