12.2.2. Part 2: Expansion Cohort

Upon completion of cohort expansion in Part 1 and the totality of data supports opening Part 2, GCB-DLBCL and tFL patients in both mutation status, as well as patients with MM will be enrolled at RP2D for Part 2 study. There are 5 cohorts in Part 2, i.e. 2 cohorts for GCB-DLBCL patients (mutant and wild type), 2 cohorts for tFL patients (mutant and wild type), and 1 cohort for MM patients.

For each of GCB-DLBCL and tFL cohorts, at least 10 subjects and up to 32 subjects will be enrolled at the RP2D (including subjects enrolled in the previous stage), using decision rules defined in [Table 17](#). The sample size and stopping rules are based on the methodology of Lee & Liu [[Lee](#), 2008].

The assumptions underlying the design are detailed below for GCB-DLBCL and tFL cohorts. The null hypothesis is:

$$H_0: p \leq 20\%$$

The alternative hypothesis is:

$$H_A: p \geq 40\%$$

As listed in [Table 17](#), the futility/efficacy evaluation will start with 10 subjects and until maximum of 32 subjects. This design allows to stop early for futility only. The design will have a type I error rate (α) of 0.066 and a power of 0.801. The trial may be stopped early for futility if the predictive probability of the overall response rate greater than the null hypothesis of 20% is below 10% for this design. The type I error rate, power, and predictive probability of success were derived by explicitly stating null and alternative hypothesis of response rate, the minimum and maximum sample size, futility and efficacy stopping boundaries and the selection of the optimizing criterion as the maximization of power under the alternative hypothesis. The Bayesian prior used in determining the design was Beta (0.15, 0.85), a distribution with a mean response rate of 15%. Under the null hypothesis, that is, if the true response rate is 20%, the expected sample size of the design is 16.06 subjects and probability of early termination (PET) is 90.8%. Under the

alternative hypothesis, that is, if the true response rate is at least 40%, the expected sample size of the design is 29.16 subjects and PET is 18.1%.

The input parameters for the design shown in [Table 17](#) are:

Nmin	10
Cohort	1
Nmax	32
theta_Lbegin	0.1
theta_Lend	0.1
theta_Lstep	0.001
theta_Upper	1
theta_Tbegin	0.9
theta_Tend	0.9
theta_Tstep	0.001
p_0	0.2
p_1	0.4
Prior a0	0.15
Prior b0	0.85
Type I Error	0.1
Power	0.8

Table 17 Stopping Rules for GSK2816126 GCB-DLBCL and tFL Cohort

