12.3.4. Interim Analysis

12.3.4.1. Part 1

Futility and efficacy interim analysis of overall response rate will be performed continuously for GCB-DLBCL expansion cohort in Part 1 of the study, after 13 subjects have been enrolled. In addition, safety, PK, and PD marker data will be examined during Part 1. Prior to determining the GSK2816126 dose for the next cohort, exploratory analyses will be conducted to assess the relationship of GSK2816126 dose levels with safety, PK and PD parameters using all data from available cohorts. If success criteria are reached at an interim analysis for GCB-DLBCL at MTD/RP2D twice-weekly every 3 out of 4 weeks followed by 1 week off, and the totality of data support opening Part 2, then Part 2 will begin and Part 1 expansion will close.

Full details of procedures and of the analyses planned at the interim analysis will be provided in the Reporting and Analysis Plan (RAP).

12.3.4.2. Part 2

For each expansion cohort, after the initial 10 subjects have enrolled at the RP2D dose, response data will be reviewed on an ongoing basis and the number of responses observed will be compared with the stopping rules provided in Section 12.2.2. In addition, safety, PK, and PD marker data will be analyzed. Full details of procedures and of the analyses planned at the interim analysis will be provided in the Reporting and Analysis Plan (RAP).

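### The stated type I error of 0.066 and power of 0.801 do not describe the two Part 2 GCB-DLBCL cohorts, which reuse the Part 1 subjects whose responses help open Part 2

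*Protocol*

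**What the plan says.** **Gate.** Section 3.4 makes Part 2 follow a notable response rate in the Part 1 GCB-DLBCL expansion. The Table 16 footnote in Section 12.2.1.2 links reaching the efficacy count to opening Part 2. Section 12.3.4.1 says that if the success criteria are reached at an interim analysis "and the totality of data support opening Part 2, then Part 2 will begin and Part 1 expansion will close". Section 3.3.7 is softer: once the bound is reached, Part 2 may be opened.

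**Reuse.** Section 3.4 says that earlier patients at "MTD/RP2D in the previous stages of the trial (dose escalation and cohort expansion in Part 1) will be included for the Part 2 analysis". Section 12.2.2 counts previous-stage subjects inside the 10 to 32 per GCB-DLBCL or tFL cohort.

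**Hypotheses and error.** The null (ORR at most 20%) and the alternative (at least 40%) are the same in Part 1 and in each Part 2 GCB-DLBCL cohort (Sections 12.1.1 and 12.1.2). Section 12.2.2 states for Table 17 a "type I error rate (α) of 0.066 and a power of 0.801", with no allowance for the gate.

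**Head count.** Section 12.2 speaks of "The additional 168 subjects in Part 2 of the study". In Section 5.1 the components sum to the stated maximum only if all 168 are new: 40 + 27 + 15 + 168 = 250.

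**The concern.** An error rate derived for a cohort starting at 0 responders out of 0 is attached to cohorts that start with a block of subjects chosen, in part, because many of them responded. Part 2 is meant to characterise activity separately in mutant and wild-type disease, with ORR as its primary endpoint. Its result is read only if Part 2 has opened. In that setting part of the evidence is the evidence that opened it, so a success is easier to reach under the null than 0.066 suggests, and the ORR estimate is pulled upward.

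**Working it through.** **Inputs.** Tables 16 and 17 (Section 12.2); p0 = 0.20 and p1 = 0.40; GCB-DLBCL mutant share 18/83 = 21.7%, or about 22% (Section 3.5.2), varied from 10% to 30%. Part 1 enrols regardless of mutation status (Section 3.5.2).

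**Method.** Exact binomial recursion. Let f(n, x) be the probability of x responders among n subjects with no stop so far:

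f(n, x) = (1 − p)·f(n−1, x) + p·f(n−1, x−1)

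States at or beyond a bound are removed at each n where the table applies. In Table 17, success means passing every futility bound and ending with at least 10/32.

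**Step 1: the protocol's own figures, from 0/0.**

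| Design | Type I error | Power | Expected N (null / alternative) |
|---|---|---|---|
| Table 16 | 0.0865 (stated 0.087) | 0.803 (stated 0.803) | 16.48 / 16.98 |
| Table 17 | 0.0660 (stated 0.066) | 0.801 (stated 0.801) | 16.06 / 29.16 |

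The arithmetic in Section 12.2.2 is right for an unselected cohort that starts empty.

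**Step 2: what is carried forward at a true ORR of 20%.** Part 1 cohorts that cross the efficacy bound average 18.5 subjects, and the mean of their observed ORRs is 42%. At a 21.7% mutant share, about 18.5 × 0.783 = 14.5 go to the wild-type cohort and 18.5 × 0.217 = 4.0 to the mutant cohort.

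**Step 3: one case by hand.** Suppose 6/13, all wild type, is carried forward. Reaching 10/32 needs at least 4 responders among 19 new subjects. With X ~ Bin(19, 0.20), P(X ≥ 4) = 0.545. Applying the Table 17 futility bounds on the way lowers this to 0.53.

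**Step 4: all crossing paths.** Each Part 1 path that crosses is weighted by its probability. Its subjects are split by mutation status (binomial) and its responders by group (hypergeometric). Each cohort then continues under Table 17. At a true ORR of 20%, given that Part 2 opens:

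| Mutant share | Wild-type false success | Mutant false success |
|---|---|---|
| 10% | 0.55 | 0.10 |
| 21.7% | 0.450 | 0.137 |
| 30% | 0.39 | 0.17 |

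At 21.7% these are 0.450/0.066 = 6.8 and 0.137/0.066 = 2.1 times the stated value. The mean wild-type ORR at the end of the cohort (at 32 or at a futility stop) is 29.5%, against a truth of 20%.

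**Step 5: over the whole trial**, multiplying by the chance that Part 2 opens:

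- True ORR 20%: wild type 0.0865 × 0.450 = 0.039; mutant 0.0865 × 0.137 = 0.012.
- True ORR 40%: wild type 0.803 × 0.936 = 0.75; mutant 0.803 × 0.829 = 0.67. Here 0.936 and 0.829 are the chances of success given opening.

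**Step 6: Table 17 on new subjects only.** Given opening, 0.066 and 0.801 hold exactly. Over the whole trial the error is 0.0865 × 0.0660 = 0.0057 and the power is 0.803 × 0.801 = 0.64.

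**The case against.** The best defence is that type I error is normally the chance, under the null, that the trial declares success. In that frame the gate more than offsets the reuse: 0.039 and 0.012 lie below 0.066, and no mutant share pushes a single cohort above 0.0575. A final stage that keeps earlier data always has a conditional error above nominal, and cumulative use is openly planned here. This part of the defence stands. A reader might infer that the trial's false-positive rate is inflated overall, and the documents do not support that.

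A reader might also infer that crossing Table 16 is a strict and sole condition for opening Part 2. The text is looser. Section 3.3.7 says only that Part 2 may be opened, and Sections 3.2 and 12.2.2 name the totality of data without a response count. If opening did not depend on response at all, reuse alone would leave 0.066 intact. However, the only route described in terms of response counts is the efficacy bound, and Section 3.4 asks for a notable response rate, so selection on response remains.

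A third tempting reading starts from Section 7.6.1.2, where "EZH2 mutation analysis on archival tumor samples or fresh biopsies from subjects enrolled in Part 1 may also be performed": that allocation of Part 1 subjects to cohorts would depend on who happened to be tested. The Time and Events table requires tissue from all GCB-DLBCL subjects for central EZH2 testing, so this is not a sound basis for criticism.

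What the defence does not remove is that 0.066 and 0.801 are the error and power of these two cohorts in neither frame, and that the pooled ORR is biased once Part 2 has opened.

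**Conclusion.** The concern holds for the two GCB-DLBCL cohorts, as a statement about results read after Part 2 has opened. There, the chance of false success at a true ORR of 20% is about 0.45 (wild type) and 0.14 (mutant) rather than 0.066, and the wild-type ORR is overestimated by about 9.5 percentage points (29.5 − 20). Over the whole trial the error is lower than stated, and success at a true ORR of 40% is about 0.75 and 0.67 rather than 0.801.

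These figures assume that the Table 16 gate and all futility bounds are followed as written, that the true ORR is the same in both mutation groups, that all Part 1 subjects in the gate are carried forward, and that each cohort runs to 32 unless stopped. A looser gate would bring the conditional figures closer to the stated ones. Subjects carried into the tFL and MM cohorts were not selected by this gate, so their stated figures are not affected by it.

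Separately, Section 12.2 (168 additional subjects) and Section 12.2.2 (cohort sizes that include earlier subjects) cannot both be right. This is a smaller point, since the totals are approximate ceilings, but it decides how many new subjects each cohort gets.

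**What to change.** 1. In Section 12.2.2, for the two GCB-DLBCL cohorts, replace 0.066/0.801 with operating characteristics computed for the gated design with reuse, both given that Part 2 opens and over the whole trial. Keep the present figures for tFL.
2. In Sections 3.4 and 12.3.5.4, report ORR in subjects first dosed after Part 2 opens beside the pooled ORR, and state that the pooled ORR is biased upward by the gate.
3. Reconcile the additional 168 of Section 12.2 with the inclusive cohort sizes of Section 12.2.2.

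These are wording changes plus a short calculation. Items 1 and 2 need no extra subjects.

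An option, not a requirement, is to apply Table 17 to newly dosed subjects only. That restores 0.066/0.801 once Part 2 is open, but lowers whole-trial wild-type power from about 0.75 to 0.64. It fits within the 250 if the 168 are all new; under the wording of Section 12.2.2 it would mean recruiting replacements for the carried subjects.
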